4. OBJECTIVES AND ENDPOINTS

Objectives	Endpoints
Primary	
To assess the long-term safety and tolerability of RVT-101	Incidence of AEs and changes in physical examinations, vital signs measurements, ECGs, clinical laboratory assessments, and C-SSRS results
Secondary	
To assess the effects of RVT-101 on subject dependency as measured by the Dependence Scale (DS)	DS score change from baseline at Weeks 28 and 52
To assess the effects of RVT-101 on quality of life as measured by the EuroQOL 5 dimensions questionnaire (EQ-5D)	EQ-5D score change from baseline at Weeks 28 and 52

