6.3. Exclusion Criteria

A subject will be excluded from participation in this study if any of the following criteria apply:

1. Subject experienced an uncontrolled AE in the lead-in study that would preclude continuation in a 12-month open label extension study, in the opinion of the Investigator. Subjects who experienced an SAE during the lead-in study may be considered for participation in this study only after discussion with the Medical Monitor.
2. Subject has a clinically significant vital signs or ECG abnormality at the end of the lead-in study, or at the Screening visit for this study, that would preclude continuation in a 12-month open label extension study, in the opinion of the Investigator.
3. Subject has a clinically significant laboratory abnormality at V7 or V8 of the lead-in study, or at the Screening visit for this study, that would preclude continuation in a 12-month open label extension study, in the opinion of the Investigator. Investigators need not wait for V8 results before enrolling the subject in this study. However, any clinically significant abnormality subsequently identified from V8 of the lead-in study and/or at the Screening visit for this study will be evaluated by the Investigator for continued involvement in this study.
4. Subject has developed any confounding medical or psychiatric condition that would preclude continuation in a 12-month open label extension study, in the opinion of the Investigator.
5. Significant suicide risk as defined by suicidal ideation as endorsed on items 4 or 5 on the C-SSRS at Screening of this study, or clinical assessment of significant suicidal risk.
6. Treatment with any concomitant medication detailed in Table 1.
7. Confirmed corrected QT interval (QTc) value \geq to 450 msec for males or \geq 470 msec for females. Subjects with a QRS value greater than 120 msec and QTc value less than

500 msec may be eligible following discussion with the Medical Monitor.

8. Subject is unable to take the investigational product as prescribed throughout the study (with assistance is acceptable).
9. Subject or caregiver is an immediate family member or employee of the participating investigator, any of the participating site staff, or of the sponsor study staff.

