10.4. Key Elements of Analysis Plan

All safety measures over the course of the study will be presented. Data will be listed and tabulated by the treatment groups assigned in the lead-in study and by overall; descriptive statistics will be presented for all safety parameters. Continuous data will be summarized by means, SDs, medians, maximum, minimum, and number of subjects. Categorical data will be summarized by counts and percentages. No inferential statistical analyses of safety parameters will be conducted.

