10.4.2.2. Clinical Laboratory Tests

Summaries of clinical laboratory data will be provided for subjects in the Safety Population.

Quantitative values and change from baseline in quantitative values will be summarized by planned visit for each quantitative laboratory value. Listings of all laboratory results and reference ranges will be provided. For multiple lab assessments at the same visit, the worst value will be used for the data summaries.

Laboratory values that fall outside of the reference range will be flagged as H=High or L=Low. A lab shift table may be provided to show the baseline to the worst post baseline value. Laboratory values that do not meet the laboratory abnormalities will be assigned N=normal in the shift table.

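### Laboratory results are classed only as High, Low or Normal, so the plan commits to no count of subjects by degree of abnormality that is independent of investigator judgement

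*Combined protocol and SAP*

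**What the plan says.** Section 4 makes laboratory change part of the primary safety endpoint: "Incidence of AEs and changes in physical examinations, vital signs measurements, ECGs, clinical laboratory assessments, and C-SSRS results". Section 10.4.2.2 gives the rule for classing a result: "Laboratory values that fall outside of the reference range will be flagged as H=High or L=Low". The remaining values form the third class: "Laboratory values that do not meet the laboratory abnormalities will be assigned N=normal in the shift table". The table built on these classes is not a commitment: "A lab shift table may be provided to show the baseline to the worst post baseline value".

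The same section plans two other outputs. One is a by-visit summary: "Quantitative values and change from baseline in quantitative values will be summarized by planned visit for each quantitative laboratory value". Section 10.4 fixes the statistics for it: "Continuous data will be summarized by means, SDs, medians, maximum, minimum, and number of subjects". The other is a full listing: "Listings of all laboratory results and reference ranges will be provided". Where a visit has several results, the worst one is summarized.

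Exclusion criterion 3 in Section 6.3 begins "Subject has a clinically significant laboratory abnormality at V7 or V8 of the lead-in study". It applies only where the investigator considers that the abnormality rules out continuing in the extension. Subjects with out-of-range values can therefore enter.

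Sections 8.2.1.1.1 and 8.2.1.6 require clinically significant laboratory abnormalities to be recorded as AEs, and Section 10.4.2.1 tabulates AEs. No section of the supplied document gives a multiple of a reference limit, a grade, a fold-change criterion or a combined liver criterion.

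**The concern.** A one-year safety study should be able to say how many subjects had a marked laboratory change, and in which lead-in group. Three classes cannot say this. In a subject who starts above the upper limit, any further rise stays in the same class. In a subject who starts normal, a trivial excursion and a tenfold one land in the same cell.

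Baselines above the limit should be expected, because criterion 3 screens on clinical judgement and not on the reference range. V1 may also coincide with the last on-treatment visit of a lead-in study that used the same 35 mg dose (Sections 3.3 and 8.1). For subjects who received RVT-101 there, a mild rise that began in the lead-in becomes part of the extension baseline, and its later progression reads H to H.

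Liver tests show what is at stake. Table 2 schedules serum chemistry at every visit from V1 to V7 and at unscheduled visits, and Table 3 includes ALT, AST, alkaline phosphatase, bilirubin and GGT. The data for a graded count would exist, but the plan does not commit to producing one.

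**Working it through.** The plan states no figure on this point to reproduce: the study is descriptive, and 1150 is an enrolment ceiling that follows from lead-in completion (Section 10.2). The check applies the Section 10.4.2.2 rule to example subjects.

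**Step 1: the classification rule.** Let x be the result divided by the upper reference limit (ULN). The class is H if x > 1 and otherwise N; low values are not at issue here. The shift compares baseline with the worst post-baseline value. The example values and the graded bands in the last column are assumptions for illustration; the documents give neither.

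| Baseline → worst (× ULN) | Fold rise | Shift under the plan | Shift under assumed bands |
|---|---|---|---|
| 1.1 → 1.2 | 1.09 | H → H | >1–3 → >1–3 |
| 1.1 → 3.5 | 3.18 | H → H | >1–3 → >3–5 |
| 1.1 → 11 | 10.0 | H → H | >1–3 → >10 |
| 0.9 → 1.05 | 1.17 | N → H | N → >1–3 |
| 0.9 → 10 | 11.11 | N → H | N → >5–10 |

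Under the plan the first three cases read as no shift, and the last two share a cell. Graded bands separate the cases within each group.

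**Step 2: how many subjects could not show an upward shift.** Number = (proportion above ULN at baseline) × 1150. The documents give no proportion, so a range is shown:
- 2.5%: 0.025 × 1150 = 28.75, about 29 per analyte
- 5%: 0.05 × 1150 = 57.5, about 58
- 10%: 0.10 × 1150 = 115

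The pooling of marginal and marked rises in the N to H cell needs no such assumption. It can affect any subject who starts normal.

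**Step 3: whether the by-visit summaries fill the gap.** If k subjects rise from 1.1 to 11 × ULN, the mean change moves by k × (11 − 1.1)/n.
- k = 1, n = 1150: 9.9/1150 = 0.0086 × ULN
- k = 5, n = 1150: 49.5/1150 = 0.043 × ULN
- k = 1, n = 575 (an assumed lead-in group of half the ceiling): 9.9/575 = 0.017 × ULN
- k = 5, n = 575: 49.5/575 = 0.086 × ULN

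The mean hardly registers such cases. The maximum does: a single such subject makes the maximum change at that visit at least 9.9 × ULN. But the maximum is the same whether one subject or five reached that value, and it cannot show whether ALT and bilirubin rose in the same subject. These summaries are also by planned visit, so the plan does not ensure that a peak found at an unscheduled visit enters them.

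**The case against.** The strongest objection is that marked changes already have a route into the tables. Section 8.2.1.1.1 defines a clinically significant finding broadly, as anything that affects management, including extra monitoring or tests. It expressly covers a previously abnormal test that now needs further action, which is the high-to-much-higher case. Section 8.2.1.6 asks for clinically significant results to be repeated until they normalize, return to baseline or stabilize. Section 10.4.2.1 then tabulates AEs by term, maximum severity and relationship. The maxima and listings would show an extreme value, and the Safety Monitoring Committee receives data in the form it requests (Section 8.2.1.2).

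All of this stands, and it rules out two stronger readings that a reader might infer. One is that the plan would hide a marked rise: it would not, because the full listings contain it. The other is that the plan yields no count of important laboratory changes at all: AE counts are planned.

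The AE route still does not supply the missing output. It rests on judgement at about 185 centers with no numeric limit. The severity grades in Section 8.2.1.1.4 turn on daily activities, clinical status and need for intervention, not on the size of the laboratory change, so a marked rise without symptoms could be graded mild. Counts taken from listings afterwards would use limits chosen after the data were seen.

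A second objection is that a separate SAP may hold graded criteria. Section 10.4.3 leaves room for further analyses there, and no separate SAP laboratory section is in the supplied text, so this cannot be checked. However, Sections 10.4.1 and 10.4.2.4 expressly defer detail to the SAP, and Section 10.4.2.2 does not.

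Finally, the supplied text reports no hepatic signal for RVT-101, and none should be inferred from the use of liver tests as the example.

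**Conclusion.** The point holds in a limited form. For the laboratory part of the primary safety endpoint, the plan commits to no count of subjects by degree of abnormality that is independent of investigator judgement, and to none for concurrent transaminase and bilirubin rises. Even the coarse three-class shift table is not guaranteed.

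That rising subjects already above the limit read H to H, and that marginal and marked rises from normal share a cell, follows directly from the stated rule. The 29, 58 or 115 subjects per analyte rest on assumed baseline rates and on enrolment reaching the ceiling of 1150. They describe one optional table, not all laboratory reporting. This is a worthwhile and cheap improvement to a descriptive safety analysis. It is not evidence that a safety problem would go unseen.

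**What to change.** In Section 10.4.2.2 and the SAP:

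- Make the shift table a commitment, and define the worst value separately as highest and lowest for analytes that can be abnormal in either direction.
- Add, by lead-in group and overall, the number and percentage of subjects whose worst post-baseline value, unscheduled visits included, crosses graded limits.
- For liver tests, express the limits as multiples of the upper reference limit, and add a combined transaminase-plus-bilirubin count.
- For subjects out of range at baseline, also count by multiples of baseline.

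The sponsor chooses and records the limits before database lock. They are reporting categories only and imply no clinical management rule. The cost is SAP wording, some programming and one or two more tables. Results and reference ranges are already collected, so nothing changes for subjects or sites.

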10.4.2.3. Vital Signs, Electrocardiograms, Physical Findings, and Other Safety Evaluations

Descriptive summaries of medical history, vital signs, weight, and ECG parameters will be presented separately for each study visit. Clinically significant abnormal ECG findings will be summarized by study visit.

Abnormal physical examination findings will be summarized to include the number and percentage of subjects experiencing each treatment-emergent abnormal physical finding.

Concomitant medications will be coded using the WHO ATC classification (http://www.whocc.no/filearchive/publications/1_2013guidelines.pdf).

10.4.2.4. Suicidality

A subject data listing of all answers of the C-SSRS questionnaire will be presented. The number and percentage of subjects reporting suicidal ideation and behavior will be summarized. Additional summaries may be provided if data warrant. Details will be provided in the Statistical Analysis Plan (SAP).

10.4.3. Other Analyses

Additional analyses of the data may be conducted as deemed appropriate and will be detailed in the SAP. Further analyses of the data not specified in the SAP may be undertaken as post-hoc analyses after completion of the study. Results of all study assessments will be included in an appendix to the study report.

11. RESPONSIBILITIES

11.1. Investigator Responsibilities

11.1.1. Good Clinical Practice

The investigator will ensure that this study is conducted in accordance with the principles of the “Declaration of Helsinki” (as amended in Edinburgh, Tokyo, Venice, Hong Kong, and South Africa), International Conference on Harmonisation (ICH) guidelines, or with the laws and regulations of the country in which the research is conducted, whichever affords the greater protection to the study subject. The investigator will ensure that the basic principles of “Good Clinical Practice,” as outlined in 21 Code of Federal Regulations (CFR) 312, subpart D, “Responsibilities of Sponsors and Investigators,” 21 CFR, part 50, 1998, and 21 CFR, part 56, 1998, are adhered to. These standards are consistent with the requirements of the European Community Directive 2001/20/EC, which shall be adhered to.

Since this is a “covered” clinical trial, the investigator will ensure that 21 CFR, Part 54, 1998, is adhered to; a “covered” clinical trial is any “study of a drug or device in humans submitted in a marketing application or reclassification petition subject to this part that the applicant or FDA relies on to establish that the product is effective (including studies that show equivalence to an effective product) or that make a significant contribution to the demonstration of safety.” This requires that investigators and all sub-investigators must provide documentation of their financial interest or arrangements with Axovant Sciences, or proprietary interests in the drug being studied. This documentation must be provided before participation of the investigator and any sub-investigator. The investigator and sub-investigator agree to notify Axovant Sciences of any change to reportable interests during the study and for 1 year following completion of the study. Study completion is defined as the date that the last subject has completed the protocol defined activities.

This study is also subject to and will be conducted in accordance with 21 CFR, part 320, 1993, “Retention of Bioavailability and Bioequivalence Testing Samples.”

11.1.2. Institutional Review Board/Independent Ethics Committee Approval

This protocol and any accompanying material to be provided to the subject (such as advertisements, subject information sheets, or descriptions of the study used to obtain informed consent) will be submitted by the investigator to an IRB or IEC. Approval from the IRB or IEC must be obtained before starting the study and should be documented in a letter to the investigator specifying the protocol number, protocol version, protocol date, documents reviewed, and date on which the committee met and granted the approval.

Any modifications made to the protocol or other documents described in the above paragraph after receipt of IRB or IEC approval must also be submitted to the IRB or IEC for approval before implementation.

11.1.3. Informed Consent

The investigator is responsible for obtaining written informed consent from each individual participating in this study after adequate explanation of the aims, methods, objectives, and potential hazards of the study and before undertaking any study-related procedures. The investigator must utilize an IRB- or IEC-approved consent form for documenting written informed consent. Each informed consent will be appropriately signed and dated by the subject or the subject's legally authorized representative and the person obtaining consent. Consent from both the caregiver and subject will be obtained.

11.1.4. Confidentiality

The investigator must assure that subjects' anonymity will be strictly maintained and that their identities are protected from unauthorized parties. Only subject initials, date of birth, and an identification code (ie, not names) as permitted by national regulations should be recorded on any form or biological sample submitted to the sponsor, IRB or IEC, or laboratory. The investigator must keep a screening log showing codes, names, and addresses for all subjects screened and for all subjects enrolled in the trial.

The investigator agrees that all information received from Axovant Sciences, including but not limited to the Investigator's Brochure, this protocol, eCRFs, the investigational product, and any other study information, remain the sole and exclusive property of Axovant Sciences during the conduct of the study and thereafter. This information is not to be disclosed to any third party (except employees or agents directly involved in the conduct of the study or as required by law) without prior written consent from Axovant Sciences. The investigator further agrees to take all reasonable precautions to prevent the disclosure by any employee or agent of the study site to any third party or otherwise into the public domain.

11.1.5. Study Files and Retention of Records

The investigator must maintain adequate and accurate records to enable the conduct of the study to be fully documented and the study data to be subsequently verified. These documents should be classified into at least the following 2 categories: (1) investigator's study file, and (2) subject clinical source documents.

The investigator's study file will contain the protocol/amendments, eCRF and query forms, IRB or IEC and governmental approval with correspondence, informed consent, drug records, staff curriculum vitae and authorization forms, and other appropriate documents and correspondence.

The required source data should include sequential notes containing at least the following information for each subject:

- Documentation that subject meets eligibility criteria, i.e., history, physical examination, and confirmation of diagnosis (to support inclusion and exclusion criteria);
- Participation in trial (including trial number);

- Trial discussed and date of informed consent;
- Dates of all visits;
- Documentation that protocol specific procedures were performed;
- Results of safety parameters, as required by the protocol;
- Start and end date of investigational product (including dose regimen, dispensing and return);
- Record of all AEs (start and end date, causality and intensity);
- Concomitant medication (including start and end dates, dose, and dose changes);
- Date of trial completion and reason for early discontinuation, if applicable.

All clinical study documents must be retained by the investigator until at least 2 years after the last approval of a marketing application in an ICH region (i.e., United States, Europe, or Japan) and until there are no pending or contemplated marketing applications in an ICH region; or, if no application is filed or if the application is not approved for such indication, until 10 years after the investigation is discontinued and regulatory authorities have been notified. Investigators may be required to retain documents longer if required by applicable regulatory requirements, by local regulations, or by an agreement with Axovant Sciences. The investigator must notify Axovant Sciences before destroying any clinical study records.

Should the investigator wish to assign the study records to another party or move them to another location, Axovant Sciences must be notified in writing in advance.

If the investigator cannot guarantee this archiving requirement at the study site for any or all of the documents, special arrangements must be made between the investigator and Axovant Sciences to store these in sealed containers outside of the site so that they can be returned sealed to the investigator in case of a regulatory audit. When source documents are required for the continued care of the subject, appropriate copies should be made for storage outside of the site.

11.1.6. Electronic Case Report Forms

For each subject enrolled, an eCRF must be completed and signed by the principal investigator or sub-investigator (as appropriate) within a reasonable time period after data collection. This also applies to records for those subjects who fail to complete the study (even during the screening period if an eCRF was initiated). If a subject withdraws from the study, the reason must be noted on the eCRF. If a subject is withdrawn from the study because of a treatment-limiting AE, thorough efforts should be made to clearly document the outcome.

11.1.7. Drug Accountability

The investigator or designee (ie, pharmacist) is responsible for ensuring adequate accountability of all used and unused investigational product. This includes acknowledgment of receipt of each shipment of investigational product (quantity and condition), subject dispensing records, and

returned or destroyed investigational product. Dispensing records will document quantities received from Axovant Sciences and quantities dispensed to subjects, including lot number, date dispensed, subject identifier number, subject initials (if permitted by national regulations), and the initials of the person dispensing the investigational product.

The investigator or his/her designee will be responsible for maintaining accurate records of investigational product dispensing and collection and for returning all unused investigational product to Axovant Sciences or its designee at the end of the study. The instructions and address for returning unused investigational product will be provided in a separate document.

All investigational product supplies and associated documentation will be periodically reviewed and verified by the study monitor over the course of the study.

